**Integrated Treatment (CBTI-PE):** The integrated treatment uses the core components of CBT-I and PE, with the goal of enhancing both insomnia and PTSD outcomes. Integrated treatment will be delivered in 14 90-minute weekly sessions. CBTI-PE (see Table 3 for full outline of protocol) starts with VA rollout CBT-I for the first 3 weeks with a focus on the effects of PTSD on insomnia. PE protocol (psychoeducation) begins on week 4 of treatment and both treatments overlap till week 6 when CBT-I ends and the active treatment of PE begins (i.e., imaginal and in-vivo exposures). However, CBT-I sleep diary review and sleep time adjustment will continue till the end of treatment to increase adherence to the sleep schedule. The timing of integrated treatment will allowing appropriate time for CBT-I to influence sleep efficiency before PE exposures start. Final session 14 includes reviewing goals from treatment, discussing progress and concrete skills to be used post-treatment, and discussing relapse prevention and handling reemergence of insomnia or PTSD symptoms. The integrated manual was developed and piloted with two subjects (see Preliminary Studies 2a.2) diagnosed with comorbid insomnia and PTSD at the VASDHS.

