8-13	CBT-I: Review sleep diary; problem solve any difficulties in completing sleep assignments; modify TIB based on SE PE: Review in-vivo exposures; continue in-vivo and imaginal exposures; focus in in-vivo on both reducing avoidance and increasing healthy interactions	-Track sleep with diary -Adhere to sleep restriction schedule and stimulus control -Continue In-vivo exposures -Listen to Imaginal exposure tape
14	General: Review goals from treatment, discuss progress, and concrete skills to be used post-treatment CBT-I: Discuss relapse prevention and handling reemergence of insomnia PE: Final imaginal exposure; discuss how to handle reemergence of PTSD symptoms	N/A

Control Non-Active Sleep Treatment (Sleep hygiene education). We have included a non-active control arm to allow for the dose response of CBTI-PE to just PE alone. The non-active sleep control condition used in this study is a manualized protocol developed by [name] (Mentor) for use in his ongoing HSR&D funded Merit Award examining the efficacy of CBT-I delivered via telemedicine (see Table 4 for weekly Hygiene protocol). The protocol is matched to CBTI-PE for number of sessions and length of sessions, however the content is modified to exclude the active components of standard CBT-I treatment. The sleep education control sessions focus on reviewing sleep diaries, providing information on relationship between sleep disturbance and PTSD, presentation of sleep hygiene education, and reviewing daily stressors that may impact sleep. [name] (mentor) showed in a recent trial that sleep hygiene had no effect on insomnia; the pre- to post-treatment means (SD) on the Pittsburgh Sleep Quality Index in participants randomized to the proposed non-active intervention were 12.9 (3.3) and 11.8 (3.8), respectively (p > 0.05). In addition, patients rated the treatment as having high credibility, suggesting that this treatment condition was successful as a non-active treatment. Following completion of participation, enrollees in the sleep hygiene education group will be offered a clinical referral to the Sleep program at the VASDHS for CBT-I.

Table 4. Hygiene-PE Protocol

Week	Content	Homework
1	General: Establish rapport; motivational enhancement for Insomnia	-Track sleep with sleep
	and PTSD treatment; review goals for Insomnia and PTSD	diary

	Sleep Education: Review psychoeducation about insomnia; provide information on relationship between sleep disturbance and PTSD PE: N/A	

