estimate of the individual variability around the population trend, the variability of the individual intercepts (baseline values) and slopes (changes across time), and the correlation between them. The model will include a random intercept, a random effect for assessment time, and fixed effects for comparison groups and group-by-time interaction. A fully saturated treatment by time model will be utilized for inference. Co-variance structure will be chosen based on Akaike's Information Criterion (AIC) and *compared to each other using a chi-square test*. Random group level treatment effects will also be evaluated for importance based on the model AIC. This allows for any group level effects to be incorporated into the model. Data will be analyzed from all randomized subjects using all available data collected at baseline, post-treatment, and at follow-up. The models will be expanded to determine an adjusted intervention difference by including additional covariates such as *gender, age, medications, pain, and depression*. A chi-square test will compare attrition rates between groups.

Secondary Aim 2: Examine the effects of sleep efficiency on PTSD outcomes at post-treatment.

Hypothesis Aim 2: *All Veteran's CAPS-5 scores will decrease from pre- to post-treatment.* However, Veterans who demonstrate larger increases in sleep efficiency will exhibit lower PTSD symptoms at the end of treatment compared to Veterans with lower sleep efficiency.

Independent variables: Sleep Efficiency (sleep diary) at week 6, *Pre-treatment CAPS-5 scores*

Dependent variables: CAPS-5 scores at post-treatment.

Covariates: *age, gender, medications, pain, depression.*

Analyses Aim 2: A multivariate regression equation will be used to statistically test this hypothesis. Regression analyses will be used to examining the relationship between SE at week 6 on follow-up CAPS-5 scores controlling for pre-treatment CAPS-5 scores. A significant finding for SE will indicate that Veterans who are sleeping more efficiently at week 6 of treatment has an additive influence on the effectiveness of PE.

Secondary Aim 3 (Moderator): Determine the extent to which SE and changes in PTSD symptoms relate to global quality of life outcomes.

Hypothesis 3: *There will be an interaction effect of SE at post-treatment and changes in PTSD symptoms from pre- to post-treatment predicting quality of life outcomes.*

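### SAP Aim 2 hypothesises about increases in sleep efficiency but models only the week-6 level, without baseline SE or arm, names two outcome times, and fixes in advance a reading the model cannot support

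*SAP*

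**What the plan says.** All the core text is in the SAP under Secondary Aim 2.

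- **Hypothesis.** Veterans with "larger increases in sleep efficiency will exhibit lower PTSD symptoms at the end of treatment compared to Veterans with lower sleep efficiency". The first half concerns change; the comparator is a level.
- **Predictors.** "Independent variables: Sleep Efficiency (sleep diary) at week 6", together with pre-treatment CAPS-5. The covariates are age, gender, medications, pain and depression. Neither list contains baseline SE, SE change or treatment arm.
- **Outcome.** The variable list has "Dependent variables: CAPS-5 scores at post-treatment"; the analysis sentence has "SE at week 6 on follow-up CAPS-5 scores controlling for pre-treatment CAPS-5 scores". Under Aim 1 the SAP defines these as separate visits, at 14 and 28 weeks.
- **Reading rule.** "A significant finding for SE will indicate that Veterans who are sleeping more efficiently at week 6 of treatment has an additive influence". The influence meant is on how well PE works.

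Protocol 2a.3.g describes the arms. In CBTI-PE, "PE protocol (psychoeducation) begins on week 4 of treatment and both treatments overlap till week 6", and "CBT-I sleep diary review and sleep time adjustment will continue till the end of treatment". Of the control: "The protocol is matched to CBTI-PE for number of sessions and length of sessions". Table 4 lists only PE for its weeks 4 to 14. Protocol 2a.3.f provides a 7-day baseline diary and tracks adherence to assignments every other week.

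**The concern.** CAPS-5 is adjusted for its baseline; SE is not. A Veteran who always slept efficiently and one whose sleep improved to the same level look identical to this model, so it does not test the part of the hypothesis about increases.

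SE is also not randomised. Its coefficient can differ from zero, with no effect of SE on PTSD, for three reasons: stable baseline SE differences that predict outcome; arm effects on CAPS-5 by routes other than SE; or common causes of week-6 SE and CAPS-5 that are not in the model, such as adherence. The reading rule leaves no room for any of these.

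The Protocol's section on relevance to the VA mission says that understanding sleep as a mechanism of change for PE will guide later research. A secondary association reported as sleep adding to PE would feed directly into that. The two outcome times also leave an analyst free to choose between visits.

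**Working it through.** **1. The plan's own figure.** The SAP gives no figure for Aim 2. Its stated size is 34 per group (d = 0.8, two-sided alpha 0.05, power 90%). Normal approximation: n = 2(1.960 + 1.282)²/0.8² = 32.8, so 33. The two-sample t-test gives 33.8, so 34, with power 0.902. Allowing for 25% drop-out, 68/0.75 = 90.7, against 90 planned. The figure reproduces, but it powers the comparison of arms. It supplies the n = 68 used below; n = 52, the follow-up number in Protocol 2a.3.b, was also run.

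**2. Level as a stand-in for increase.** With equal variances and baseline-to-week-6 correlation ρ, level and change correlate at √((1 − ρ)/2). For assumed ρ of 0.3, 0.5 and 0.7 this is 0.59, 0.50 and 0.39.

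**3. Size, by simulation.** Ordinary least squares, 6,000 trials per scenario, 34 per arm, SAP covariates included. Every effect size is an assumption. The documents' only diary SE data are three uncontrolled pilot cases (73.30% to 91.07%, a gain of 17.77 points), which give no between-arm shift.

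- Correlations: CAPS0–depression 0.5, CAPS0–pain 0.3, depression–pain 0.3, SE0–CAPS0 −0.2, SE0–depression −0.2, SE0–pain −0.1, SE0–SE6 0.5.
- Post CAPS = 0.5·CAPS0 + 0.1·depression + 0.1·pain + scenario effects + residual, total SD about 1.
- Shift means the between-arm difference in week-6 SE, in SD.

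Percentage of trials with a significant week-6 SE term:

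| Scenario | SAP model | + baseline SE | + arm only | + both |
|---|---|---|---|---|
| *No true SE effect* | | | | |
| No other route, shift 0.8 | 5.4 | 5.1 | 5.4 | 5.3 |
| Baseline SE predicts CAPS at 0.2, shift 0.8 | 14.0 | 5.1 | 15.2 | 5.3 |
| Non-SE arm benefit 0.3, shift 1.2 | 12.1 | 13.4 | 5.4 | 5.3 |
| Non-SE arm benefit 0.5, shift 1.2 | 23.5 | 26.3 | 5.4 | 5.3 |
| Unmeasured common cause 0.3/−0.3, shift 1.2 | 12.0 | 13.1 | 14.6 | 17.0 |
| Unmeasured common cause 0.5/−0.4, shift 1.2 | 40.3 | 45.3 | 51.2 | 61.8 |
| *True slope −0.30, shift 1.2* | | | | |
| No arm route | 90.7 | 84.1 | 79.6 | 68.2 |
| Opposite arm effect 0.3 | 72.1 | 58.1 | 79.6 | 68.2 |
| Opposite arm effect 0.5 | 52.3 | 36.0 | 79.6 | 68.2 |

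For the baseline route, the SAP model's rate runs from 12.5% to 14.9% over shifts of 0.5 to 1.2, and from 8.6% to 22.7% over SE0–SE6 correlations of 0.3 to 0.7. At n = 52 it is 11.2%, against 5.6% with baseline SE.

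In the masking case with an opposite arm effect of 0.3, the true −0.30 is estimated at −0.233 (SAP), −0.219 (+ baseline SE) and −0.301 (with arm).

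Repeating key scenarios with separate code gave similar values: about 14% and 5% for the baseline route; power 93%, 88% and 75% (SAP, + baseline SE, + both) with no arm route; 76% falling to 61% under masking at 0.3; and 35%, 40% and 56% for the stronger common cause.

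**The case against.** **The aim may be about level.** The aim, the comparator, the predictor and the reading rule can all be read as level statements. If baseline SE predicts outcome, a week-6 level association is real. This stands in part: the 14% is an error rate only for a claim about change or cause. But the hypothesis does say increases, and the reading rule is a claim about influence.

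**Timing is partly protected.** Protocol 2a.3.g schedules CBT-I to act on SE before exposures begin; imaginal exposure starts in week 7 and in-vivo homework in week 6. In CBTI-PE this limits early PE response as a common cause. Table 4 gives no such weekly detail for the control, and adherence is untouched.

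**The repair has costs.** This stands. Baseline SE lowers power and worsens masking, and with an unmeasured common cause the added terms raise false positives, substantially at the stronger loadings. Arm adjustment can also remove real mediation.

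**Follow-up may be loose wording.** Probably, since the other Aim 2 lines say post-treatment or end of treatment. The SAP defines the two visits separately, so the lines still need aligning.

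Three stronger readings are tempting and not supported:

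- *Arm alone would make SE significant in about 62% of trials.* This takes the 2.15 effect on insomnia indices, of unstated type, as a week-6 SE shift, and sends all of d = 0.8 around SE. The documents support neither step.
- *Omitting arm chiefly creates false positives.* Matched session length with shared time in CBTI-PE points, if anything, towards masking. Even that rests on one line of Table 4, which does not prove that the control has no sleep work after week 3.
- *Item overlap between CAPS-5 and sleep drives the result.* The SAP already plans every analysis with the sleep items removed.

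**Conclusion.** The point holds from the text alone. Aim 2 does not test the increases in its own hypothesis, names two outcome visits, and commits to a conclusion that an association with a non-randomised week-6 measure cannot carry. The SAP's mention of group assignment under Missing Data concerns drop-out and does not put arm into this regression.

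The size is illustrative. If baseline SE predicts CAPS-5 at 0.2 SD beyond the listed covariates, the planned model rejects a true null for SE in roughly one trial in seven rather than one in twenty. With no such route, its rate is the nominal 5%. Nothing in the documents fixes which case applies, so confidence in the magnitude is medium at best.

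This should be changed, but it does not threaten the trial's main result: Aim 2 is secondary and the randomised Aim 1 comparison is unaffected. A reader might infer that the added terms would make a causal reading safe. They would not: under a common cause every version rejects too often.

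**What to change.** 1. Add baseline diary SE as a covariate in the primary Aim 2 model, so that the week-6 coefficient addresses change. The diary is already collected, and Aim 1 needs it.
2. Pre-name one sensitivity model that also adds treatment arm. The model without arm carries the Aim 2 test. If the two disagree, report that the association cannot be separated from arm.
3. Replace the reading rule with: *week-6 SE, adjusted for baseline SE, is associated with post-treatment CAPS-5; this does not by itself show that sleep adds to PE.*
4. Use post-treatment CAPS-5 in every Aim 2 line.

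**Cost.** SAP wording, one covariate and one extra reported model; no new data. Under the assumed effects at n = 68 (slope −0.30, shift 1.2 SD), power falls from about 91–93% to 84–88% with baseline SE, and to 68–75% with arm as well. At n = 52 the corresponding figures are 80%, 72% and 55%. The two models can therefore disagree through lost power alone, so disagreement is not evidence against an SE effect. If an opposite non-SE arm effect of 0.3 SD exists, baseline SE alone lowers power from about 72–76% to 58–61%, which is why the arm model is shown. With an unmeasured common cause, false positives go from about 11–12% to 13% and 17% (loadings 0.3/−0.3), or from 35–40% to 40–45% and 56–62% (0.5/−0.4). The softer wording in step 3 is therefore essential.

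**Minor side notes.** Table 5 and the diary paragraph in Protocol 2a.3.i list no baseline diary and should be aligned with 2a.3.f. The Aim 3 main-effect regressions could include the baseline WHOQOL-BREF already collected.

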#### Insomnia: Relevance to VA and to Treatment

Difficulty in sleep onset and maintenance is the most frequently reported symptom of the 17 symptoms of PTSD. Among Veterans with PTSD, sleep disturbances are nearly universal with 70 - 91% of patients with PTSD reporting comorbid insomnia. Veterans with PTSD show more trouble falling asleep, staying asleep, excessive daytime sleepiness and early morning awakenings than Veterans without PTSD.

Insomnia has also been shown to have a deleterious effect on overall health and well-being. Insomnia contributes to prospective risk of major depression,  increased psychiatric symptoms and poor coping,  and is associated with physical health complaints as well as increased risk for hypertension, cardiovascular disease,  and immunosuppression.  Notable among those negative outcomes, insomnia is highly correlated with substance abuse, impaired daytime functioning, and suicide risk. 

Insomnia also has negative health consequences over-and-above the effects of PTSD. For example, sleep impairment accounted for a significant portion of the variance in physical health complaints even after controlling for other PTSD symptoms and depression. The significant and chronic sleep loss commonly associated with PTSD contributes independently to additional negative health ramifications including pain disorders, asthma, and hypertension. Insomnia with PTSD is associated with a reduced capacity to carry out daily activities, with functional impairment and reduced quality of life. Overall, insomnia is associated with greater severity of PTSD symptoms and poorer quality of life and daily functioning.

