We will aim to recruit 2-3 participants per month for this study. [name] has recruited 4-6 participants per month with a more restricted inclusion and exclusion criteria, thus a minimum of 2-3 participants per month is feasible. Additionally, [name] is recruiting Veterans with active AUD, which we exclude for, eliminating any conflict of recruitment. The size of the proposed recruitment sample was estimated based on: (1) power analyses (see Planned Data Analysis 2a.3.j); (2) mentor experiences conducting research with similar screening procedures, designs and populations and in similar treatment settings; and (3) attrition rates reported in the literature in PTSD treatment. Based on mentors' experiences and estimates in the literature, we expect to phone screen approximately 200 Veterans to obtain 100 individuals for baseline assessment. We anticipate that 33% of Veterans will not meet inclusion/exclusion criteria following baseline assessment, resulting in 90 Veterans getting randomized to treatment. A conservatively estimated total recruitment sample of 90 will allow for up to 25% attrition, resulting in a final sample size of approximately 52 Veterans at follow-up. 52 Veterans at follow-up conservatively allow adequate power to examine all study aims.

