Study Name: Integrated CBT-I and PE on Sleep and PTSD Outcomes (Impact Study)

Document Name: Statistical Analysis Plan

NCT ID: NCT02774642

Document Creation Date: 11-20-2015

PI: [name]

Planned Data Analysis 11-13-2015

Power analyses: Sample size was determined to ensure adequate statistical power to detect between group differences in PTSD and sleep at end of treatment and 3-month follow-up. For both outcomes the effect size was estimated as d defined as $[d = |m_1 - m_2| / \sigma]$ where m_1 and m_2 are change from intake in the outcome scores of the two conditions and σ is the common within-group standard deviation of the change score.¹⁰⁹ The effect size for the between group difference in PTSD CAPS scores from intake to end of treatment was estimated from several studies that have evaluated the effect of PE^{110, 111} on PTSD. Four studies of PE have demonstrated large within group effect sizes ranging from 1.3¹¹¹ to 4.1¹¹² with an average ES of 2.5. However, given that both conditions will receive PE, and it is already known that CBTI shows large effects on insomnia (e.g., Ulmer⁸⁰ ES = 2.15), we powered on the effect of CBTI on PTSD symptoms.

Three studies reported effect sizes of CBTI on PTSD symptoms with an average ES of 1.8.⁷⁹⁻⁸¹ We conservatively used a large effect size (0.8) requiring 34 participants per group to be detected with 90% power and a two-tailed test with alpha at .05. We increased the total sample size to be randomized to $N = 90$ in anticipation of 25% study drop-out by the 3 month assessment. Overall, we believe this sample size balances three needs: (1) sufficient power to compare the study groups; (2) the reality of recruiting a sample with dual insomnia and PTSD; and (3) project cost considerations.

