Independent variables: Sleep Efficiency (sleep diary) at post-treatment, *change in CAPS-5 scores from Pre- to Post-treatment, interaction of SE and change in CAPS-5 scores.*

Dependent variables: WHOQOL-BREF at follow-up.

Covariates: *age, gender, medications, pain, depression.*

Analyses Aim 3: A multivariate regression equation will be used to statistically test this hypothesis. Four Regression analyses will be run examining the effects of SE and changes CAPS-5 scores from pre- to post-treatment on quality of life outcomes. The first two regressions will examine SE and changes CAPS-5 scores independently to predict quality of life outcomes. We expect that both SE and changes in CAPS-5 scores will generalize to quality of life as indicated by significant p values. The third regression will analyze both SE and CAPS-5 scores in the same regression model to examine the influence of sleep and PTSD symptoms together on quality of life. The final regression analysis will examine SE, changes in PTSD symptoms, and the interaction of SE and changes in PTSD symptoms on quality of life outcomes. We expect that Veterans with efficient sleep and larger decreases in PTSD symptoms will have higher quality of life at follow-up.

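### Aim 3 predicts 3-month quality of life without adjusting for baseline WHOQOL-BREF or baseline CAPS-5, so stable differences between Veterans can make the sleep-efficiency term significant with no carry-over from treatment

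*SAP*

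**What the plan says.** For Secondary Aim 3 the SAP names the outcome as "Dependent variables: WHOQOL-BREF at follow-up", which is a level and not a change. The first predictor is also a level: "Independent variables: Sleep Efficiency (sleep diary) at post-treatment". The others are the pre-to-post change in CAPS-5 and its interaction with SE. The covariates are age, gender, medications, pain and depression, with no statement of when they are measured.

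Four regressions follow: SE alone, CAPS-5 change alone, both together, and both with the interaction. The reading of the first two is fixed in advance: "We expect that both SE and changes in CAPS-5 scores will generalize to quality of life as indicated by significant p values".

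Table 5 of the protocol marks WHOQOL-BREF and CAPS-5 at baseline. Aim 2 in the same SAP controls for pre-treatment CAPS-5, and Aim 1 models baseline as a time point. The protocol background (Insomnia: Relevance to VA and to Treatment) says that "insomnia is associated with greater severity of PTSD symptoms and poorer quality of life and daily functioning".

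**The concern.** The regression of a later quality-of-life level on a later sleep level mixes two things. One is carry-over from better sleep to better quality of life. The other is that some Veterans had better quality of life and sleep from the start and kept both. The protocol's own background describes that second pattern, and without the starting value of the outcome the model cannot separate the two. The SAP nevertheless takes a significant p value as the sign that gains generalize.

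The CAPS-5 term has a related weakness. A change score entered without its baseline partly stands in for entry severity, because Veterans who start high have more room to fall. Entry severity is plausibly linked to quality of life in its own right.

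At stake is the claim that improved sleep and reduced PTSD symptoms carry over to quality of life. Aim 3 is secondary.

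**Working it through.** **1. The plan's own figures.** The SAP gives no power or sample size for Aim 3. Its one calculation is "We conservatively used a large effect size (0.8) requiring 34 participants per group", at 90% power and two-sided alpha .05. The two-sample t-test gives 33.8, so 34 per group is reproduced (33 by the normal approximation). Allowing for 25% drop-out, 68 / 0.75 = 90.7, against 90 planned. Then 90 × 0.75 = 67.5, so N = 68 is used at follow-up. Protocol 2a.3.b instead says "resulting in a final sample size of approximately 52 Veterans at follow-up", so N = 52 is shown as well. These two figures need reconciling, but the conclusion is the same under either.

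**2. Assumptions.** The documents give no correlations. Let a be the correlation of baseline quality of life with post-treatment SE (0.2 to 0.4), and b its correlation with follow-up quality of life (0.5 to 0.7). SE has no effect of its own, so SE and follow-up quality of life correlate only through the baseline, at ρ = a × b.

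**3. SE term, no covariates.** With z = atanh(ρ) × √(N − 3), the rejection probability is about Φ(z − 1.96) + Φ(−z − 1.96). Example: ρ = 0.3 × 0.6 = 0.18, and z = 0.182 × √65 = 1.47, giving 31%.

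**4. SE term, with baseline depression and pain.** Assume these correlate −0.6 and −0.5 with baseline quality of life, and with each other only through it (0.6 × 0.5 = 0.30). Together they explain R² = (0.36 + 0.25 − 2 × 0.6 × 0.5 × 0.30) / (1 − 0.09) = 0.43 / 0.91 = 0.47 of it. The partial correlation is ab(1 − R²) / √[(1 − a²R²)(1 − b²R²)], and √(N − 3) becomes √(N − 5).

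| a, b | ρ | N = 68, none | N = 52, none | Partial ρ | N = 68, depression and pain | N = 52, depression and pain |
|---|---|---|---|---|---|---|
| 0.2, 0.5 | 0.10 | 13% | 11% | 0.057 | 7% | 7% |
| 0.3, 0.6 | 0.18 | 31% | 25% | 0.107 | 14% | 11% |
| 0.4, 0.7 | 0.28 | 64% | 52% | 0.175 | 29% | 23% |

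Simulation of the same settings at N = 68 (ordinary least squares) agrees: about 13, 30 and 66% without covariates, about 9, 18 and 37% with depression alone, and about 7, 15 and 30% with depression and pain. Between separate simulations the lowest and highest rates without covariates varied by about two points, hence about 12-66%. In the simulations that recorded sign, almost all false positives were in the expected direction (better sleep, better quality of life).

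**5. SE term, with baseline WHOQOL-BREF.** The partial correlation of SE with follow-up quality of life is then zero by construction, so the rate should be 5%. Simulation gives about 5-6%.

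**6. CAPS-5 change.** Let the decrease be pre minus post, with equal SDs and a pre-post correlation of 0.5. Its correlation with quality of life is (r_pre − r_post) / √(2 − 2 × 0.5) = r_pre − r_post.

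- Only entry severity relates to follow-up quality of life: r_pre = −0.4, r_post = 0.5 × −0.4 = −0.2, difference −0.2. Simulation at N = 68 gives about 38% significant, nearly all with a larger decrease going with lower quality of life.
- Pre and post scores both correlate −0.5 with baseline quality of life: difference 0, about 5%.
- Pre −0.3 and post −0.5 with baseline quality of life (stability 0.7): difference +0.2, about 21% in the expected direction. With a post-treatment SD 1.3 times as large, about 41%.

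The sign of the bias therefore depends on quantities the documents do not give.

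**7. Interaction.** With linear effects, normal data and no true effect, the SE by CAPS-5 change term rejects in 5-6% of simulated trials without either baseline, which is close to nominal.

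**The case against.** The strongest defence has four parts.

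- **The aim is associational.** Aim 3 asks how far SE and PTSD change relate to quality of life, and its last expectation concerns the follow-up level. Adjusting for the starting level asks a somewhat different question. This stands as far as the stated aim goes. It does not cover the sentence on generalizing, which is a claim about carry-over.
- **Pain and depression already adjust for much of this.** They do in part: under the assumptions above they roughly halve the SE error rate, but it stays above 5% in every setting. The SAP also does not say when they are measured, and later values would not stand in for starting quality of life.
- **The CAPS-5 result cuts the other way.** A reader might take the 38% as further evidence that pre-existing differences will pass for recovery. It is not: nearly all of those results have the sign opposite to the SAP's expectation and would contradict the hypothesis. What remains is that the term can mask or reverse a true link as easily as create one.
- **The formal hypothesis is the interaction.** A reader might infer that the test of Hypothesis 3 is invalid. The check does not show that; in this setup its error rate is nominal. Nor is the treatment effect on quality of life in doubt, because Aim 1 tests it with baseline in the model.

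**Conclusion.** The omission is real, and it matters for the SE main effect. As specified, a significant SE coefficient cannot be told apart from stable differences between Veterans. At N = 68 the false-positive rate is about 12-66% with no covariates, about 7-30% with baseline depression and pain, and about 5-6% with baseline WHOQOL-BREF. The CAPS-5 change term is confounded, direction unknown.

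It would go too far to say that pre-existing differences will be read as recovery. They can be; how often depends on correlations that are assumed throughout (0.2-0.4 for SE with baseline quality of life, 0.5-0.7 for its stability, −0.6 and −0.5 for depression and pain). Confidence is therefore medium as to size, although the omission itself is plain in the text. This should be corrected before analysis, but it does not threaten the primary aim.

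**What to change.** In the SAP for Aim 3:

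- Add the baseline value of the same WHOQOL-BREF score to all four regressions.
- Add baseline CAPS-5 to every regression that contains CAPS-5 change.
- State that pain and depression enter at their baseline values. Table 5 marks the PHQ-9 only in the bi-weekly column, while 2a.3.f includes mood in the baseline battery, so name the measurement that serves as the depression baseline.
- Replace the statement on generalizing with one about follow-up quality of life given its starting level.

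The cost is SAP wording and at most two degrees of freedom per model. Baseline WHOQOL-BREF and CAPS-5 are already collected, so no new data are needed for them.
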